4.7.6.7 CCI [REDACTED]

Total number of CCI [REDACTED] and CCI [REDACTED] will be described overall and by treatment group.

Total number of CCI [REDACTED] per patient will be computed by summing CCI [REDACTED] form. Number of CCI [REDACTED] will be computed considering CCI [REDACTED]. Namely:

- CCI [REDACTED]

Where:

- CCI [REDACTED] = $\text{sum} \left\{ \frac{\text{CCI [REDACTED]}}{\text{CCI [REDACTED]}} \right\}$
- CCI [REDACTED] Assessment $i = \text{Coeff } i * \{(\text{part1}) [(Date of Assessment } i) - (Date of Assessment } i-1) + 1]/2 + (\text{part2}) [(Date of Assessment } i+1) - (Date of Assessment } i)]/2\}$

Where Coeff $i = 1$ if Employment status equal to Employed or Temporarily Employed at Assessment i , Coeff $i = 0$ otherwise.

Treatment results will be compared using an independent groups t-test by means of the Satterthwaite method [6]. The corresponding two-sided p-value will be presented. Mean difference, computed as colistimethate sodium - placebo, and corresponding 95% CI will also be presented.

The above summaries/analyses will be performed using the mITT Population.

Notes:

- CCI [REDACTED] of first and last assessment will include only the subsequent period (referred to in the formula as part 2) and previous period (referred to in the formula as part 1), respectively.
- CCI [REDACTED] relies on the assumption that no change in the employment status occurs during the CCI [REDACTED] computed for each assessment.

4.7.6.8 CCI [REDACTED]

The CCI [REDACTED] will be provided overall and by treatment group. Percentages will be computed on the total number of subjects with at least one pulmonary exacerbation.

CONFIDENTIAL

Sponsor:	Zambon S.p.A.	Protocol Number:	Z7224L02
----------	---------------	------------------	----------

The total number of CCI [REDACTED] per subject will be analysed using a negative binomial regression model in a similar manner as the primary endpoint with the exception that the (log) duration of subject follow up rather than the duration of exposure will be included as the offset variable. The annualised CCI [REDACTED] will be extracted from this model for both randomised treatment groups as well the ratio of CCI [REDACTED], together with its associated 95% confidence interval and p-value.

A summary table will present the number and percentages of subjects with at least CCI [REDACTED] having:

- CCI [REDACTED]
- [REDACTED]
- [REDACTED]
- [REDACTED].

The total duration of CCI [REDACTED] will be summarised by treatment group using descriptive statistics for continuous variables. This summary shall include a presentation for the following categorisations:

- CCI days;
- CCI days;
- CCI days;
- Not Evaluable.

In case of CCI [REDACTED], the duration of CCI [REDACTED] will be calculated using the following formula:

- Duration of CCI [REDACTED]

In case of missing CCI [REDACTED] or CCI [REDACTED] the CCI [REDACTED] will be classified as “Not Evaluable”.

The above summaries/analyses will be performed using the mITT Population.

4.7.6.9 CCI [REDACTED]

For the CCI [REDACTED], the score for the following domains will be calculated as follows:

- CCI [REDACTED]: items 1, 2, 3, 4, 16;
- CCI [REDACTED]: items 17, 20, 25, 27, 28;
- CCI [REDACTED] items 6, 8, 9;
- CCI [REDACTED]: items 7, 10, 11, 23;
- CCI [REDACTED]: items 18, 19, 22, 26;
- CCI [REDACTED]: items 12, 13, 14;
- CCI [REDACTED]: items 5, 15, 21, 24;
- CCI [REDACTED]: items 29, 30, 31, 32, 33, 34, 35, 36, 37.

CONFIDENTIAL

Sponsor:	Zambon S.p.A.	Protocol Number:	Z7224L02
----------	---------------	------------------	----------

Details for calculations are reported in Appendix 2: CCI [REDACTED] Version 3.1.

The CCI [REDACTED] domain scores assessed at Visits 3 - 7 (End of Treatment) will be summarised by treatment group using descriptive statistics including 25th and 75th percentiles. Results for absolute changes from baseline will also be reported. Due to CTP amendments and to the corresponding changes in the procedures schedule, not all the subjects have undergone the same sequence of assessments. All the values collected will be summarised jointly. Considering the presence of a stratified and permuted blocks randomisation list no imbalance between treatments is expected.

Change from baseline in each CCI [REDACTED] domain score will be analysed using a linear mixed model for repeated measures including treatment, visit, treatment-by-visit interaction, use of stable concomitant therapy with oral macrolides and country, as detailed in CCI [REDACTED], as fixed effects and baseline value as covariate. An unstructured covariance matrix will be assumed and the Kenward-Roger adjustment will be used for the degrees of freedom. The least square means in each treatment group, the least square mean differences between treatments, their 95% CIs and associated p-values overall and at each visit will be estimated by the model. The OBSMARGINS option will be used.

The above summaries/analyses will be performed using the mITT Population.

4.8 Safety Analysis

All safety variables will be summarised overall and by treatment group using the Safety Population.

The safety variables are:

- AEs;
- Spirometry results;
- CCI [REDACTED] CCI [REDACTED]
- Vital signs;
- Physical examination results;
- Haematology and clinical chemistry parameters;
- 12-lead ECG parameters.

4.8.1 Adverse Events

An AE is "any untoward medical occurrence in a subject or clinical trial subject administered a medicinal product and which does not necessarily have a causal relationship with this treatment".

An AE will be regarded as treatment-emergent if it has an onset date on or after the date of first IMP dose. For AEs with onset date on day of first IMP dose, the variable "Prior to first IMP administration?" in the Adverse Events eCRF form will be considered. AEs prior to first IMP administration will be considered as non-treatment-emergent. All other AEs, i.e. AEs with negative or missing answers to the question "Prior to first IMP administration?" will be considered as TEAEs. Partially missing dates will be handled as outlined in Section 4.11. If an

CONFIDENTIAL

Sponsor:	Zambon S.p.A.	Protocol Number:	Z7224L02
----------	---------------	------------------	----------

AE has a partial or fully missing date, and it is unclear whether the AE is treatment-emergent, it will be assumed that it is.

Only TEAEs will be included in the AE and SAE summaries. Non-treatment-emergent events will be included in the subject listings and flagged but not included in the summaries.

A summary table will present the number and percentage of subjects reporting:

- Any TEAEs;
- Any TEAEs by severity;
- Any TEAEs by relationship to IMP;
- Any TEAEs by action taken with IMP;
- Any Serious TEAEs;
- Any Fatal TEAEs.

The number of events occurring will also be reported.

Related AEs are those events for which there is a reasonable possibility that the IMP caused the event. When relationship to IMP is missing for a TEAE it will be imputed to be drug-related. Every effort should be made to query the site for complete data entry prior to database lock.

Fatal AEs are those reported with an outcome of “Fatal”.

The number (and percentage) of subjects experiencing at least one TEAE, along with the number of events occurring, will be summarised by MedDRA SOC and PT, overall and by maximum severity.

A subject with more than one occurrence of the same AE in a particular SOC or PT will be counted only once in the total of those experiencing AEs in that particular SOC or PT. Two AEs with the same SOC or PT will be considered as two different events when calculating the “number of events” in the tables.

For summaries by maximum severity, if a subject experiences more than one event in the same SOC and PT, the subject will be counted in the maximum severity but all the events will be reported in their severity level. Maximum severity will be ranked as follows: severe > moderate > mild > unknown.

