10.1.6. SAFETY EVALUATIONS

Adverse Events

AEs will be recorded by the Investigator in the appropriate eCRF Section starting with the date of informed consent until the follow-up phone call. At each contact (i.e. clinical visit or phone call), subjects will be asked in a non-leading manner if they experienced any AEs.

All AEs occurring from the day of the first IMP administration, i.e. Visit 2, until the end of the trial, i.e. follow-up phone call, will be considered as TEAEs.

(Note: A pulmonary exacerbation will be reported as an AE or serious AE [SAE]; pulmonary exacerbations will also be captured as efficacy assessments.)

For definitions and reporting of AEs and SAEs, see [Section 17](#).

Lung Function by Means of Spirometry

Spirometry measurements of FEV₁ and FVC (predicted values will be as per GLI reference equations; <http://gligastransfer.org.au/calcs/spiro.html>) [21] will be performed at Visit 1 (if not performed in the preceding 30 days) to verify the eligibility of the subject (see inclusion criteria in [Section 8.2.1](#)), and at Visit 2 through Visit 7.

Lung function measurement and daily calibration of the spirometer will be performed according to the standardised methods described by the American Thoracic Society/European Respiratory Society. It is suggested that, in each centre, the model of the spirometer used does not change during the study.

Lung function measurements will be done at approximately the same time of the day during clinic visits (dependent on IMP administration) with subjects either standing or sitting (for each subject, this should be consistent throughout the trial) with the nose clipped after at least 10 minutes rest. Calibration of the spirometer must be performed preferably by the same Investigator at each visit prior to spirometry measurements and the reports must be kept with the source trial documents, if printouts are generated. If calibration printouts cannot be generated and the spirometer is not self-calibrating, it must be documented on paper that the calibration was performed properly.

For FEV₁ and FVC, the highest value from 3 technically satisfactory attempts will be considered (irrespective of the curve they come from).

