17.8.1. REPORTING SERIOUS ADVERSE EVENTS

Investigators must report SAEs **within 24 hours of first becoming aware of the event**.

The SAE must be reported through the eCRF to the CRO's Pharmacovigilance group as given in the contact details provided in the "List of Zambon/CRO personnel" at the beginning of this CTP.

If there is any issue with the electronic reporting process, such as internet failure or database issues, this must not delay SAE reporting. The back-up procedure is to send the back-up paper SAE Form to the CRO's Pharmacovigilance group by email or fax using the following contact details:

Email: CCI [REDACTED]
Fax: CCI [REDACTED]

Note: Any reports submitted on paper must be retrospectively added to the eCRF as soon as possible.

The community standards of confidentiality must always be maintained and any relevant national legislation on data protection must be followed.

SAEs are reportable from the time a subject signs the informed consent to the follow-up phone call 2 weeks after the last dose of IMP.

If the Investigator becomes aware of any SAE occurring to a subject within the follow-up window established in this CTP, he/she will report the SAE as above. The SAE will also be reported in the eCRF.

If the Investigator becomes aware of any SAE outside the follow-up window established in this CTP, it is the Investigator's responsibility to report the SAE to the CRO. The Investigator might use the eCRF, as described above. However, the SAE is not an event which occurred within the trial period.

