19.4.3. SAFETY DATA

All safety endpoints will be summarised and analysed using the Safety Population.

Incidence of Treatment Emergent Adverse Events

The number and the percentage of subjects reporting TEAEs, treatment emergent SAEs, severe TEAEs, TEAEs leading to discontinuation and TEAEs leading to death will be presented by treatment group, along with the number of events occurring.

TEAEs will also be summarised by System Organ Class and Preferred Term according to MedDRA; they will additionally be summarised by severity and relationship to treatment. A separate summary table will be provided for SAEs.

Only TEAEs, i.e. events with an onset date on or after the date of IMP start, will be included in the summary tables. Individual data listings will include all AEs recorded; a separate listing will be provided for treatment-emergent SAEs.

Number of Subjects experiencing Bronchospasm Clinically or Spirometrically Determined following IMP Administration

The number of subjects experiencing bronchospasm spirometrically determined (a >15% decrease in FEV₁ – not due to poor technique - from pre-bronchodilator baseline in the 30 minutes post-IMP), or clinically determined, will be summarised by treatment. Percentages of subjects in each treatment group and the relative risk for colistimethate sodium group/placebo group will be provided with 95% CI. Treatment differences will be assessed using a Fisher Exact test.

The number and the percentage of subjects experiencing a bronchospasm following IMP administration as clinically determined will also be reported.

In addition, the results for FEV₁ and FVC at each visit will be summarised by treatment. Descriptive statistics for absolute and percentage changes from baseline, i.e. Visit 2 (pre-dose measurement) will be reported.

CCI

The number and percentage of subjects whose CCI at the end of treatment (at 12 months [Visit 7]) will be presented by treatment, overall and by status of previous usage of colistimethate sodium/colistin.

Vital Signs

Descriptive statistics for vital signs at Visit 1 and Visit 7 will be presented overall and by treatment.

Physical examination data.

Descriptive statistics for physical examination data at Visit 1 and Visit 7 will be presented overall and by treatment.

Haematology, clinical chemistry and renal function tests

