4.8.1.1 Subsets for AE Descriptive Presentation

- Separate summary tables by SOC and PT will be presented for treatment-emergent SAEs.
- Separate summary tables by SOC and PT and by SOC, PT and maximum severity will be presented for related TEAEs.
- Separate summary tables by SOC and PT will be presented for treatment-emergent related SAEs.
- Separate summary tables by SOC and PT will be presented for treatment-emergent AEs leading to the permanent discontinuation of IMP. An AE leading to discontinuation is an AE with action taken with IMP equal to “Permanently discontinued”.

CONFIDENTIAL

Sponsor:	Zambon S.p.A.	Protocol Number:	Z7224L02
----------	---------------	------------------	----------

- Separate summary tables by SOC and PT will be presented for treatment-emergent fatal SAEs.
- Treatment-emergent SAEs and fatal AEs will be listed separately.
- The most frequent MedDRA PTs ($\geq 5\%$ of subjects with events in any treatment group) will be presented overall and by treatment. PTs will be used for tabulation, sorted by decreasing overall frequency.

All other information collected will be listed, as appropriate. Additionally, listings will display relative day of AE onset.

The relative day of AE onset will be calculated as follows:

- For pre-treatment AEs:
 - AE onset date - date of first IMP dose (if AE onset date is completely known);
 - missing (if AE onset date is incomplete or unknown).
- For TEAEs:
 - AE onset date - date of first IMP dose +1 (if AE onset date is completely known);
 - missing (if AE onset date is incomplete or unknown).

Notes:

- AEs will be coded using MedDRA version 19.1 or higher (please refer to the final Data Management Plan for the latest coding information).
- Terms will be displayed in descending overall frequency (and then alphabetically) of SOCs and in descending overall frequency (and then alphabetically) of PTs within each SOC.

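### The treatment-emergent period has no end date in SAP 4.8.1 or protocol 19.4.3, but protocol 10.1.6 closes it at the follow-up call; late SAEs or deaths entered in the eCRF would be tabulated as treatment-emergent

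*SAP*

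**What the plan says.** SAP 4.8.1 defines the flag by its start alone: "An AE will be regarded as treatment-emergent if it has an onset date on or after the date of first IMP dose". For events on the day of first dose, the eCRF question on timing decides; "All other AEs, i.e. AEs with negative or missing answers to the question" are treated as TEAEs, again with no end date. The flag then governs the output: "Only TEAEs will be included in the AE and SAE summaries". SAP 4.8.1.1 builds the serious, related, serious-related and fatal subsets on it, for example: "Separate summary tables by SOC and PT will be presented for treatment-emergent fatal SAEs".

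The protocol says two different things. In 10.1.6, AEs are recorded "starting with the date of informed consent until the follow-up phone call", and those from the day of first administration "until the end of the trial, i.e. follow-up phone call, will be considered as TEAEs". In 19.4.3, which covers the safety analysis, the wording is open-ended: "Only TEAEs, i.e. events with an onset date on or after the date of IMP start, will be included in the summary tables".

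Protocol 17.8.1 deals with SAEs that come to light after the window. The investigator must report them to the CRO and may use the eCRF to do so, but they are placed outside the trial: "However, the SAE is not an event which occurred within the trial period".

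SAP 4.13 lists the departures from the protocol and says there are no others. The TEAE window is not among them.

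**The concern.** Protocol 17.8.1 opens a route into the database for events that the protocol itself does not regard as trial events. The SAP flag has nothing to stop them from being counted. Such events occur off drug. They become known only if a site happens to hear of them, and there is no matching follow-up in the other subjects.

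The tables affected are sensitive ones: serious, related-serious and fatal events. SAP 4.8.1 also imputes a missing relationship as drug-related, so a late SAE without a causality assessment would go into the related-SAE table. The tables might then not match the period in protocol 10.1.6, and a reader of the report would have no declared change to explain the difference.

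**Working it through.** No figure in the plan needs reproducing. The check compares the rules and adds date arithmetic to show how far apart they are.

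**1. End of the treatment-emergent period in each place**

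- Protocol 10.1.6: the follow-up call.
- Protocol 17.8.1: SAEs are reportable up to the same call; later ones lie outside the trial period.
- Protocol 19.4.3: none stated.
- SAP 4.8.1: none stated.
- SAP 4.1.11, 4.8.1.1 and 4.11: none stated. The relative-day rule in 4.8.1.1 has two classes, pre-treatment AEs and TEAEs, and no post-treatment class. By contrast, 4.1.11 does close the window for exacerbations, at treatment completion or discontinuation.
- SAP 4.1: data from withdrawn subjects are used up to withdrawal unless stated otherwise. Whether 4.8.1 states otherwise is not said.

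The conflict is therefore protocol 10.1.6 and 17.8.1 on one side, and protocol 19.4.3 and SAP 4.8.1 on the other.

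**2. Length of the 10.1.6 window.** Inputs: 12 months of treatment, taken as 365 days; Visit 7 allowed ± 1 week; call 2 weeks ± 3 days after IMP is stopped (protocol 9.5 and 9.6).

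- Latest call with Visit 7 on time: 365 + 14 + 3 = 382 days.
- Latest call with Visit 7 a week late: 365 + 7 + 14 + 3 = 389 days.

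For a subject on this schedule, an SAE 390 days after first dose is outside the 10.1.6 period but meets the SAP 4.8.1 rule.

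**3. How long a late event could go on qualifying.** Inputs: trial start in Q1 2018 (protocol 7.2); up to 45 days from screening to randomisation; study closure on 28 February 2022 (SAP 4.7.4.2). Assumptions: the first subject was screened in Q1 2018 and treated for 12 months.

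- Earliest case: randomised 1 January 2018, treatment ends 1 January 2019, latest call 18 January 2019. To 28 February 2022 is 1137 days; 1137 / 30.4375 = 37.4 months.
- Latest case: screened 31 March 2018, randomised 45 days later on 15 May 2018, treatment ends 15 May 2019, latest call 1 June 2019. To 28 February 2022 is 1003 days; 1003 / 30.4375 = 33.0 months.

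For the earliest completers, then, the gap between the two rules runs to about 33 to 37 months. This is a length of time, not a count of events.

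**4. What could enter during that time.** Routine AE recording stops at the call, so non-serious AEs have no planned route in. SAEs and deaths do, through 17.8.1, if the site uses the eCRF.

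**The case against.** The best defence is that the SAP follows the protocol's own analysis section. Protocol 19.4.3 governs the summary tables and has no end date either. This stands as a correction of emphasis: a reader might infer that the SAP departed from a clear protocol rule, but the protocol disagrees with itself. The SAP is still the place to settle the matter, and it repeats one side without comment.

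Second, data collection already limits most of the exposure. This also stands. A reader might infer that late SAEs are in fact being counted. The documents support only that they would be counted if entered; eCRF entry after the window is optional. For withdrawn subjects, SAP 4.1 can be read as excluding events after withdrawal. That reading does not cover completers. Taken literally for AEs, it would also drop events between withdrawal and the call that 10.1.6 counts, which adds a third possible end date.

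Third, a reader might infer that late events pull the arms together. The documents do not show this. The AE tables are counts and percentages with no planned test of AE incidence, and equal additions to both arms dilute a ratio but leave a difference in counts unchanged. With few events, chance could move the comparison either way.

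Fourth, over-inclusion is the more cautious error for safety, and late events can be traced: listings give the relative day of onset, and SAEs and deaths are listed separately. This is fair. It is why late events should be moved to a flagged listing rather than removed, with any judged related to IMP shown there.

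**Conclusion.** The inconsistency is real and minor. Protocol 10.1.6 and 17.8.1 close the period at the follow-up call; protocol 19.4.3 and SAP 4.8.1 leave it open; SAP 4.13 declares no change. Followed as written, SAP 4.8.1 would classify any later off-drug SAE or death in the eCRF as treatment-emergent, contrary to 10.1.6. This is clearest for completers.

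The number of such events is not in the documents. A count could be produced by assuming an off-drug SAE rate and a share of sites that hear of later events, but neither input is given, so it would not be evidence of size. The number is probably small, because only SAEs and deaths qualify and entry is optional. Even so, one late death entered would change the fatal table. The primary and secondary efficacy analyses are not affected.

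**What to change.** In SAP 4.8.1:

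- Define a TEAE as an AE with onset on or after the first IMP dose and on or before the follow-up call, as in protocol 10.1.6.
- If no call was made, or if Visit 7 was split, end the window 2 weeks + 3 days (17 days) after the last actual administration in any record, including the supervised in-clinic dose. Do not use the date derived in SAP 4.1.9. For split visits that rule can take the penultimate logged date as the last dose, and a window run from it could cut off events that follow a real later dose given to test for bronchospasm.
- State that this rule overrides SAP 4.1 for AEs after withdrawal.
- Keep the existing worst-case rule for partial or missing dates.
- List and flag later SAEs and deaths separately, including any judged related to IMP.

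Reconcile the rule with protocol 19.4.3 and record the choice in SAP 4.13.

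The cost is a short rule in the SAP and one date condition in the program. The downside is that a few late events move from the summary tables to a separate listing.

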Sample Size:	A total of 420 randomised patients (210 per group) is foreseen assuming a withdrawal rate of approximately 20%, to achieve approximately 170 completed patients per group. For the primary endpoint of frequency of exacerbation (FOE), and a Poisson regression allowing for over-dispersion for FOE, with a two-sided significance level of 0.05, a treatment effect of 35% and a follow-up time of 1 year, with an FOE of 1.09 in the placebo group, this sample size will provide a power of 90%. If the treatment difference effect size is 30% between the colistimethate sodium and placebo groups, the power with 170 completed patients per group will be 80%. It is anticipated that a blinded review of the exacerbation rate across treatment groups will be conducted prior to the end of enrolment to determine whether the FOE is in line with these assumptions, given the potential impact of Covid-19. The sample size will then be recalculated and, in addition, take into consideration treatment exposure for withdrawn subjects at that stage.

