If subjects need to be CCI [REDACTED] for intravenous antibiotics, they should be visited by the research staff for an assessment within 72 hours of admission (where possible). If the subject is CCI [REDACTED] that is not the investigational site, the assessments should be carried out (where possible) by the CCI [REDACTED] under the direction of the investigational site. These assessments will include those collected during exacerbation visits/contacts and will include details regarding any interruption of IMP administration. In these circumstances, every effort should be made to complete all assessments although it is recognised that this might not be possible.

Telephone calls will be made to patients on a weekly basis during a NCFB pulmonary exacerbation until resolution to assess the progression of symptoms and to determine whether systemic antibiotic treatment is ongoing. A telephone script will be provided to sites and responses to standardised questions will be collected in relevant eCRFs.

Resolution of a NCFB pulmonary exacerbation is defined as the date of completion of the required course of systemic antibiotic treatment or the Investigator's judgement that the NCFB pulmonary exacerbation has resolved, whichever is later. This is also the end date of the corresponding AE. Exacerbations occurring less than 14 days after the end of a course of systemic antibiotics for a NCFB pulmonary exacerbation will be considered as a single event (see [Section 10.1.5](#)).

IMP administration may be temporarily interrupted during the time of systemic antibiotic treatment due to a pulmonary exacerbation based on the Investigator's judgement; thereafter, the study treatment should restart as soon as possible. Stop date and re-start date will be recorded in the relevant eCRF. The occurrence of a pulmonary exacerbation does not mandate the discontinuation of the subject from the trial and/or study treatment, unless it occurs between Visit 1 and Visit 2 and/or the Investigator believes discontinuation is in the subject's best interest.

The following assessments will be performed at an Exacerbation Visit or Phone contact, and all details of the pulmonary exacerbation have to be recorded:

- start date and duration of all symptoms since the start;
- all symptoms present which support the NCFB pulmonary exacerbation diagnosis;
- all concomitant medications, especially systemic antibiotics;
- physical examinations and vital signs (if attending the clinic);

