In the case of a partial onset date of NCFB pulmonary exacerbation due to missing day, the onset of the event will be assumed to be the first day of the month. If the resultant derived date is prior to the date of first IMP dose, then it will be assumed to be equal to the first IMP dose date. Resultant derived dates will be reviewed during the blind review meeting and documented in the Blind Data Review and Analysis Sets Report.

In case of a partial resolution date of NCFB pulmonary exacerbation due to missing day, the resolution of the event will be assumed to be the last day of the month. If the resultant derived date is after the treatment completion/discontinuation date, then it will be assumed to be equal to the treatment completion/discontinuation date.

In case a NCFB pulmonary exacerbation presents a symptom with missing duration, following a conservative approach, the longest duration based on the start and stop dates of that symptom and until the resolution date of the NCFB pulmonary exacerbation will be imputed.

Two NCFB pulmonary exacerbations will be considered as a single episode in the statistical analysis if the second exacerbation started less than 14 days after the end of the systemic antibiotic therapy for the previous exacerbation (start date of the exacerbation - end date of the treatment of the previous exacerbation $<$ 14 days). In case of more than two exacerbations for the same subject, this rule will be applied iteratively (therefore, more than two exacerbations may be considered as a single episode). Such cases will be discussed during the blind review of the data and the decisions taken will be documented in the Blind Data Review and Analysis Sets Report.

The above rule will not apply to the analysis of NCFB pulmonary exacerbations as AEs in the safety analysis.

In case of NCFB pulmonary exacerbations considered as a single episode:

CONFIDENTIAL

Sponsor:	Zambon S.p.A.	Protocol Number:	Z7224L02
----------	---------------	------------------	----------

- the start date of the first event will be considered as the start date;
- the stop date of the last event will be considered as the stop date;

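### Exacerbations count in the pooled adverse-event totals and no exacerbation-free total is planned, so a working drug lowers its own any-TEAE percentage

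*SAP*

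**What the plan says.** Protocol 10.1.6 records each exacerbation twice: "A pulmonary exacerbation will be reported as an AE or serious AE [SAE]; pulmonary exacerbations will also be captured as efficacy assessments". SAP 4.7.4 merges exacerbations that start within 14 days of the end of antibiotics for the primary endpoint, then adds: "The above rule will not apply to the analysis of NCFB pulmonary exacerbations as AEs in the safety analysis". So the SAP means exacerbations to be in the safety analysis, each counted separately.

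SAP 4.8.1 limits the AE and SAE summaries to treatment-emergent events and sets no other restriction. Its overall display is introduced by "A summary table will present the number and percentage of subjects reporting", and event counts are added. An exacerbation enters as follows:

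- Any TEAE, and the event counts: always.
- Serious, severe, related, fatal, and the various action-taken categories: when the event meets that row's criterion.

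SAP 4.8.1 and 4.8.1.1 also plan tables by system organ class (SOC) and preferred term (PT) for all, serious, related, related serious and fatal TEAEs and for those leading to discontinuation. The table list in 5.3.4 matches. Neither the text nor the list contains a TEAE or SAE total without exacerbations.

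Protocol 9.7 states that "IMP administration may be temporarily interrupted during the time of systemic antibiotic treatment due to a pulmonary exacerbation", so some exacerbations will also appear in the action-taken row. SAP 2.1 requires every exacerbation to be linked to its AE, and SAP 4.5.5 already uses the AE number to make that link.

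**The concern.** The any-TEAE percentage is the safety figure most often read first and carried into summaries. Here it includes an event that the drug is meant to prevent. If the drug is effective, the active arm loses some subjects from this row for a reason unrelated to tolerability. Equal or similar totals would then not show that the arms have similar frequencies of other adverse events.

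The planned tables do not let a reader undo this. The SOC/PT tables show the exacerbation term on its own line, but a subject can have both an exacerbation and another TEAE. The number with at least one other TEAE therefore cannot be found by subtracting that line from the total. One line also does not capture every such event: Protocol 9.7 and SAP 2.1 count pneumonia, and COVID-19 with exacerbation symptoms requiring antibiotics, as exacerbations, and these may code to other terms.

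**Working it through.** **Inputs.** Protocol section 3 (Sample Size) gives "a treatment effect of 35% and a follow-up time of 1 year, with an FOE of 1.09 in the placebo group", a two-sided 0.05 level, and 170 completers per group. It states 90% power at a 35% reduction and 80% at 30%. The variances are redacted (Protocol 19.3, SAP 3.9); the text says only that over-dispersion is mild. The documents give no expected share of subjects with a TEAE other than an exacerbation, so that share, q, is assumed.

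**Step 1: reproduce the stated power and back out k.** For a Wald test on the log rate ratio, variance = (1/μ0 + 1/μ1 + 2k)/n, with μ0 = 1.09 and n = 170. Here μ1 is 0.65 × 1.09 = 0.7085 or 0.70 × 1.09 = 0.763.

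At k = 0.30 and 35%: variance = (0.917 + 1.411 + 0.600)/170 = 0.01723, SE = 0.1313. Then 0.4308/0.1313 − 1.96 = 1.32, so power is 90.7%.

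| k | Power at 35% | Power at 30% |
|---|---|---|
| 0 (Poisson) | 95.7% | 87.6% |
| 0.264 | – | 80.0% |
| 0.30 | 90.7% | 79.0% |
| 0.337 | 90.0% | – |
| 0.50 | 86.8% | 73.5% |
| Stated | 90% | 80% |

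A gamma-Poisson simulation at k = 0.30, tested with over-dispersed Poisson, gives 90.3% and 78.8%. A k of about 0.30 fits both stated powers; k = 0 does not.

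**Step 2: subjects with at least one exacerbation in a year.** p = 1 − (1 + kμ)^(−1/k), with k = 0.30:

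- Placebo: 1 − 1.327^(−3.333) = 61.1%.
- Active, 35% reduction: 1 − 1.21255^(−3.333) = 47.4%.
- Active, 30% reduction: 1 − 1.2289^(−3.333) = 49.7%.

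**Step 3: the excess that leaves the any-TEAE row equal.** If other TEAEs are independent of exacerbations, any-TEAE = 1 − (1 − q)(1 − p). The arms are equal when

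q1 − q0 = (1 − q0) × [1 − (1 − p0)/(1 − p1)].

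The bracket is 1 − 0.3894/0.5260 = 0.260 at 35%, and 1 − 0.3894/0.5031 = 0.226 at 30%.

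| Assumed q0 on placebo | Excess at 35% | Excess at 30% |
|---|---|---|
| 30% | 18.2 points | 15.8 points |
| 60% | 10.4 points | 9.0 points |
| 80% | 5.2 points | 4.5 points |

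Example: with q0 = 60% and a 35% reduction, placebo any-TEAE is 1 − 0.40 × 0.3894 = 84.4%. With no excess of other harm, active is 1 − 0.40 × 0.5260 = 79.0%. With 70.4% having another TEAE on active, the active total is also 84.4%.

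**Step 4: sensitivity.**

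- Shorter follow-up. SAP 3.9 says recruitment stopped at 287 of 420 and subjects were recalled by the end of February 2022. SAP 4.7.4.2 says not all will have 365 days. At an assumed mean of 0.8 year and k = 0.30, the excess over both effect sizes is 7.7–15.5 points for q0 of 60–30%, and 3.9–4.4 at 80%.
- Phase 2 proportions. Protocol section 4 gives 42/71 = 59.2% on placebo and 36/73 = 49.3% on active. The bracket is 1 − 0.4085/0.5068 = 0.194, which gives 13.6 points at q0 = 30%, 7.8 at 60% and 3.9 at 80%.

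**Step 5: SAEs.** An exacerbation is serious only if it meets a criterion in Protocol 17.4.1, such as hospitalisation. No readable section gives a rate of serious exacerbations, so no size follows.

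**The case against.** The strongest case against is that little is concealed. PT rows for cough, hypersensitivity and other terms are not diluted by exacerbations, and PTs at 5% or more in any group have their own table. Bronchospasm is a separate safety endpoint, with percentages, a relative risk and Fisher's exact test at Visit 7 (SAP 4.8.2). Related-TEAE tables take an exacerbation only if it is judged related or its relationship is missing. SAP 4.5.5 already reports IMP interruptions overall and due to exacerbation. No test is planned on the any-TEAE row. Counting deterioration of the primary illness as an AE follows Protocol 17.1. All of this stands, and it confines the point to the pooled totals.

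A reader might go further and infer that these specific harms would be hidden, or that every AE table is affected alike. The documents do not support either reading, for the reasons just given.

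A reader might also infer a larger figure. Plain Poisson counts at 35% and q0 = 30% give 22.2 points, but Poisson implies 95.7% power against the stated 90%. Strong over-dispersion (k = 1) fits no better, with 77% and 62% against 90% and 80%.

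Finally, removing linked events also removes pneumonia and some COVID-19 events. Qualifying episodes count irrespective of cause (Protocol 10.1.5), so some respiratory events that the drug might have caused could be removed too. That stands, and it is why the repeat tables must accompany the planned ones and show what was taken out.

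**Conclusion.** The point holds for the pooled totals. The any-TEAE row and the event counts always include exacerbations. The serious, severe and action-taken rows include them when the criterion is met. No exacerbation-free version is planned, and none can be rebuilt from the PT rows. An effective drug therefore improves its own any-TEAE figure.

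The size of about 9–18 percentage points is an illustration for the any-TEAE row only. It rests on k near 0.30 inferred from the stated power, a full year, independence, and the assumed 30–60% background. The documents give nothing from which to check the last two. A higher background or shorter follow-up reduces it, as shown. It should not be carried over to SAEs: the direction would be the same if the drug also reduces serious exacerbations, but the size is unknown.

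This is a cheap improvement to the presentation of safety. It does not correct an error in any planned test.

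**What to change.** Keep every planned table. In SAP 4.8.1 and 5.3.4, add:

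1. A repeat of the overall TEAE summary, excluding AEs linked to a Pulmonary Exacerbation form.
2. A repeat of the SAE table by SOC and PT, with the same exclusion.

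Define the exclusion by the AE-number link in SAP 4.5.5. State that it also removes pneumonia and COVID-19 events recorded as exacerbations. Within these tables, show the excluded linked events by PT and arm so that nothing is lost.

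The cost is SAP wording and two tables, with no new data. The small downside is that they have to be read beside the all-event tables. If the blind has already been broken, SAP section 1 requires the additions to be marked as post hoc.
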